- j. All study materials (refer to Sections 4.4.2 and 4.4.3) must be returned to the Sponsor at the end of the study.
- k. Complete the following visit eCRFs:
 - 3-Month Follow-up Visit
 - Exit Visit (if there is an ongoing AE at the time of the 3-month visit, do not complete the Exit Visit and follow up via Unscheduled visit (s) instead
 - Collect Adverse Events

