#### **4.4. Study Intervention and Concomitant Medications**

##### **4.4.1. Extent of Exposure**

As is customary for contact lens solution trials, treatment exposure will not be summarized.

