#### **4.8.2. Trend Analysis Profile**

For each treatment arm, a Trend Analysis Profile will be created to assist in the identification of trends, as per FDA guidance for contact lens care products. This will include summaries of the following, for each scheduled visit individually and overall:

- Total # of eyes (active or discontinued)
- Number of discontinued eyes
- Average wear time
- Number of lens replacements
- Number of total TEAEs
- Number of corneal ulcers
- Number of iritis episodes
- Corneal staining reports:

- Total number
- Total > Grade 2
- Total # of eyes
- Edema reports (for each of epithelial edema and epithelial microcysts):
  - Total number
  - Total > Grade 2
  - Total # of eyes
- Injection reports (for each of limbal and bulbar injections):
  - Total number
  - Total > Grade 2
  - Total # of eyes
- Upper lid tarsal conjunctival abnormalities reports:
  - Total number
  - Total > Grade 2
  - Total # of eyes
- Corneal neovascularization reports:
  - Total number
  - Total > Grade 2
  - Total # of eyes
- Corneal infiltrates reports:
  - Total number
  - Total > Grade 2
  - Total # of eyes
- Total visits
- Total missed visits

For mapping purposes, and for accounting for unscheduled events, the following assignments will be used, which maps a given day to its closest visit:

Visit	Target	Mapping Unscheduled Visits
2-Week Follow-up Visit	14 Days	0 – 22 Days
1-Month Follow-up Visit	30 Days	23 – 45 Days
2-Month Follow-up Visit	60 Days	46 - 75 Days
3-Month Follow-up Visit	90 Days	76 or more Days

The number of corneal ulcers and number of iritis are a subset of TEAE, which will be identified by qualified study personnel. The number of staining, edema, injection, and neovascularization reports come from the slit-lamp examination (note edema and injection both have two reports each per slit-lamp examination).

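### The Trend Analysis Profile (SAP 4.8.2) gives raw counts over unequal time windows without time at risk, so a constant event rate would look like a trend over visits within each arm

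*SAP*

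**What the plan says.** SAP 4.8.2 states that "a Trend Analysis Profile will be created to assist in the identification of trends", separately for each arm, by scheduled visit and overall. The lines are counts: eyes, discontinued eyes, lens replacements, TEAEs, corneal ulcers, iritis episodes, several kinds of slit-lamp report, total visits and missed visits. Average wear time is also shown.

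The only rule for assigning events to visits is introduced with "For mapping purposes, and for accounting for unscheduled events". Under it, "the following assignments will be used, which maps a given day to its closest visit". The column of limits is headed "Mapping Unscheduled Visits" and reads 0-22, 23-45, 46-75 and "76 or more Days", for target days 14, 30, 60 and 90. The SAP does not say whether a TEAE is placed by its onset day or by the visit at which it was reported.

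No time at risk is planned in the profile. SAP 4.4.1 adds: "As is customary for contact lens solution trials, treatment exposure will not be summarized".

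Protocol 3.6 allows the 3-Month visit on Days 84 to 98. Protocol 6.1.4 has the used kit collected at that visit. For the Exit Visit form it instructs: "if there is an ongoing AE at the time of the 3-month visit, do not complete the Exit Visit". Such subjects continue through unscheduled visits, which fall in the open-ended last window.

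**The concern.** The profile is meant to be read along the visits, within an arm. A count read that way is informative only if each visit represents a similar amount of time at risk, or if that time is shown. Here neither holds. The windows differ in length, the last is usually the shortest and has no upper limit, and eye-days appear nowhere.

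The lines at issue are those that accrue between visits: TEAEs, ulcers, iritis, lens replacements and reports from unscheduled slit-lamp examinations. For these, the pattern over visits would mix any true change in rate with the change in window length. The last window would also mix experience on the solution with follow-up examinations made after the solution has been collected.

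**Working it through.** **Inputs.** Target days 14, 30, 60 and 90 and the window limits (SAP 4.8.2); 3-Month visit on Days 84-98 (Protocol 3.6); up to 10% losses and 340 subjects enrolled, hence 170 per arm (SAP 2.2.6). Event rates and numbers of unscheduled examinations are my assumptions, because the documents give none.

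**1. Reproduce the windows.** Assign each day to the nearest target. Ties fall on Day 22 (8 days from 14 and from 30), Day 45 (15 from 30 and from 60) and Day 75 (15 from 60 and from 90). Sending ties to the earlier visit gives 0-22, 23-45, 46-75 and 76 onward, exactly as printed.

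**2. Window lengths (inclusive).** 2-Week: 23 days, or 22 counted from Day 1, since SAP 4.1.4 calls baseline Day 1 while the table starts at 0. 1-Month: 45 - 23 + 1 = 23. 2-Month: 75 - 46 + 1 = 30. 3-Month: last day - 76 + 1, which is 9, 15 or 23 for a last day of 84, 90 or 98.

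**3. Placement by day, constant rate.** Expected counts are proportional to window length.

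| Comparison | Full follow-up | 10% losses, linear to Day 90 |
|---|---|---|
| 1-Month / 2-Week | 23/23 = 1.00 (23/22 = 1.05 from Day 1) | 0.97 |
| 2-Month / 1-Month | 30/23 = 1.30 | 1.26 |
| 3-Month / 2-Month, last day 84 | 9/30 = 0.30 | 0.29 |
| 3-Month / 2-Month, last day 90 | 15/30 = 0.50 | 0.49 |
| 3-Month / 2-Month, last day 98 | 23/30 = 0.77 | 0.74 |

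**4. Placement by reporting visit, constant rate.** The intervals between target visits are 14, 30 - 14 = 16, 60 - 30 = 30 and 90 - 60 = 30 days. The ratios are 16/14 = 1.14, 30/16 = 1.88 and 30/30 = 1.00. The fall at Month 3 disappears, and a larger step up at Month 2 replaces it.

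**5. Effect of a denominator.** Assume 0.10 TEAEs per subject over Days 0-90 (91 days), so 170 x 0.10 = 17 per arm. Placed by day, the expected counts are 17 x 23/91 = 4.3, 4.3, 17 x 30/91 = 5.6 and 17 x 15/91 = 2.8. With 0.05 per subject they are 2.1, 2.1, 2.8 and 1.4; with 0.20 they are 8.6, 8.6, 11.2 and 5.6. Divided by subject-days, the 0.10 case gives the same rate in every window, 17/(170 x 91) = 1.10 per 1,000, as it should.

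**6. Slit-lamp lines.** One examination is scheduled at each follow-up visit. Take 150 subjects and assume 0 to 0.25 unscheduled examinations each, spread evenly over the 91 days. At 0.25, Month 2 has 150 + 37.5 x 30/91 = 162.4 examinations and Month 3 has 150 + 37.5 x 15/91 = 156.2, a ratio of 0.96. At 0 the ratio is 1.00. These lines barely move.

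**7. A real late change, placed by day with the last day at 90.** A rate that doubles after Day 75 gives 30 units in Month 2 and 15 x 2 = 30 in Month 3, so the counts look flat. A rate that doubles after Day 60 gives 15 + 15 x 2 = 45 and 15 x 2 = 30, so the counts still fall.

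**The case against.** The best case for the plan has five parts.

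- **Scope.** The limits are headed as a mapping for unscheduled visits, and most lines come from scheduled slit-lamp examinations. This stands: those lines are essentially unaffected.
- **Placement.** Nothing says TEAEs are placed by onset day, so a fall at Month 3 is not built in. This also stands, but the alternative placement has its own artefact (step 4). Two programmers could produce different late patterns from the same data.
- **Between-arm reading.** Both arms use the same windows, no AE comparison is tested, and the profile feeds no success criterion. This stands in full. Only the reading over time within an arm is affected.
- **Other outputs.** A reader might infer that a late cluster of ulcers or iritis would be hidden. The documents do not support that. The AE listing in SAP 4.8.1 gives onset in days from initial use of the study device, and SAP 4.8.1.3 lists all SAEs, whose examples include iritis and presumed infectious ulcers. The timing of these events can be recovered; the profile itself does not show it.
- **Outside format.** The SAP ties the profile to FDA guidance, which is not available here. I make no claim about what that guidance requires. Adding a denominator removes none of the planned counts.

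Two further readings are tempting and go too far. One is that event counts in general rise to Month 2 and then halve. In fact the 2-Week and 1-Month counts are about level, and halving needs placement by day and a last day of 90. The other is that the windows should be redrawn so that each matches one lens pair and one kit. That cannot be done with these four visits: at the 2-Week visit the lenses are normally returned to the subject and no kit is scheduled for dispensing (Protocol 6.1.2 and Appendix A), so the first two intervals share a pair and a kit.

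**Conclusion.** The point holds for TEAEs, corneal ulcers, iritis, lens replacements and unscheduled slit-lamp reports, and only for the reading of trend within an arm. Under a constant rate with placement by day, Month 2 shows about 30% more events than Month 1, and Month 3 shows 0.30 to 0.77 of Month 2 across the allowed exit days. With placement by reporting visit, Month 2 shows about 88% more than Month 1, and Month 3 is level with Month 2.

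These figures rest on a constant rate and on follow-up ending at the 3-Month visit. Losses of 10% change them little. The open-ended last window works in the other direction for slit-lamp reports, because repeat examinations of an ongoing event can add to the total. The documents give no basis for estimating the net effect.

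This is an inexpensive improvement to a descriptive safety table. It does not threaten the trial's conclusions.

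**What to change.** In SAP 4.8.2:

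1. State that TEAEs (with the ulcer and iritis subsets) and lens replacements are placed by onset date or replacement date.
2. Add eye-days at risk in each window. Show these lines and the unscheduled slit-lamp reports both as counts and as rates per 1,000 eye-days, using subject-days for non-ocular TEAEs. If placement by reporting visit is preferred, compute the days over the intervals between visits so that numerator and denominator match.
3. Report observations made after the 3-Month or exit visit, when the study solution has been collected, in a separate post-treatment row instead of under "76 or more Days".

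The nearest-visit windows can stay.

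The cost is SAP wording and a small amount of programming; the dates needed are already collected. There are two limitations. Rates based on a handful of events will be imprecise, so the counts should remain beside them. For discontinued subjects the exit date must stand in for last use, because the date of last wear after study solution is listed only at the 3-Month visit (Protocol 6.1.4, step a).

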### **4.8.3. Clinical Laboratory Analyses**

Cultures for determining corneal ulcer or suspected ocular infection will be taken. The results of such cultures will be summarized and provided as listings. The summary will include the number of eyes with any positive culture, as well as the number and percentage of positive cultures by type (cul-de-sac, lower eyelid margin, corneal lesion, lenses, lens case, or lens case solution).

### **4.9. Other Analyses**

The following analyses will, unless otherwise specified, also be provided as listings that will include all visits. Unless stated otherwise, summaries and listings will utilize the Safety Population and be by treatment group. For summaries by visit, the “worst” measure across visits and typical measure across all follow-up visits (using the average for continuous measures, or the mode for categorical measures, as appropriate), will be summarized as well, and denoted in the listings.

Unless stated otherwise, these summaries will be by eye, rather than subject, and no comparisons between treatment group and/or baseline will be made for these analyses. Only observed cases will be used.

#### **Keratometry**

The absolute change in keratometry parameters (horizontal/vertical focusing power) at the exit visit vs. the screening/dispensing visits (diopters) will be summarized and will include a by-eye summary of the largest (absolute) change between vertical and horizontal power. This summary will be done in two ways:

- Continuous change in horizontal/vertical/largest.
- Categorical change in 1 diopter bins (i.e. 0-0.99D, 1 – 1.99D, ... ,  $\geq 5.00D$ ).

#### **Refraction**

Refraction parameters without lenses will be summarized at each visit. These parameters (in minus cylinder notation) will include sphere, cylinder, axis, and spherical equivalent.

Additionally, the change in spherical equivalent from baseline to the exit visit will be summarized both continuously and categorically by binning the change into 1-diopter bins (i.e. 0-.99D, 1 – 1.99D, ...,  $\geq 5.00D$ ).

#### **Best Spectacle Corrected Visual Acuity (BSCVA)**

The BSCVA (without lenses) will be summarized at the screening/dispensing visit and the exit visit. In addition to the letters correct, the logMAR and Snellen category parameters (see appendix) will also be summarized. The difference between the exit and screening/dispensing visit will be calculated for:

- 1) Continuous change in logMAR
- 2) Number and proportion of eyes that decrease by  $\geq 10$  letters

#### **Visual Acuity (VA)**

Separate summaries for VA will be done for worn lenses (all follow-up visits) and dispensing evaluations (1 and 2-Month Follow-Up Visits only). Summaries for worn lenses and dispensing evaluations will be summarized by subjects who (1) completed the study and (2) discontinued the study. VA will be summarized at each visit. Summaries will be done as:

- 1) LogMAR
- 2) Snellen

Additionally, the change in VA from the screening/dispensing visit will be calculated at each follow-up visit (for worn lenses). These differences will include:

- Number and percentage of eyes with a loss of  $\geq 2$  lines (note 1 line is equal to 5 letters or 0.1 logMAR)
- Categorical summary of the #lines as +4, +3, ... , -3, -4
- Continuous change in logMAR

For the final visit only, a shift table in Snellen categories from the screening/dispensing visit will be provided.

For the dispensing visit and final visit only, a summary comparing BSCVA to worn lenses VA will be provided. This will include the number and percentage of eyes with 1 or more line loss from BSCVA to worn lenses VA, and the continuous change in logMAR. A shift table comparing the initial BSCVA to final-visit worn lens VA (in logMAR increments of 0.1) will also be provided for test/control eyes who completed/discontinued the study (4 shift tables total).

### **Dispensed Lens Characteristics**

The following lens characteristics will be categorically summarized at each scheduled visit:

- Lens centration
- Lens movement
  - Josephson push up test
- Lens wettability

### **Worn Lens Characteristics**

The following lens characteristics will be categorically summarized at each scheduled visit, and will include the number of subjects who came in wearing their study lenses:

- Lens centration
- Lens movement
  - Josephson push up test
- Lens wettability
- Lens deposit type
- Lens deposit percent coverage
- Degree of front surface deposit
- Degree of back surface deposit

### **Lens Wear Parameters**

The following lens wear parameters will be summarized at each scheduled visit for each eye:

- Average daily wear time since last visit (hours per day)
- Average comfortable wear time since last visit (hours per day)
- Hours worn on day of visit (hours)
- Replaced lens (yes / no)
  - Among those with replaced lenses, time since lens replacement (days) as calculated by current visit date– date of lens replacement + 1.

A separate summary will also include summaries of the number of days on study that the subject did not wear the study lenses and the percentage of days on study that the subject used the study solution and wore their study lenses, on average (as < 80% or >=80%).

An additional summary of average wear time per visit will be provided for test/control eyes that completed/discontinued the study.

### **Over-Refraction and Distance VA for Non-Plano Eyes**

The number and percentage of eyes that are not Plano will be summarized by visit, along with their recorded sphere (D) and distance VA (total number of letters correct). This will be done by dispensed or worn lens for the appropriate visits.

### **Lens Performance Assessment**

In addition to primary endpoints “Overall comfort” and “Vision”, each of the following categories will also be summarized using the ITT Population by visit and over all scheduled follow-up visits:

- Burning and stinging upon lens insertion
- Comfort upon insertion
- **Overall comfort**
- Comfort at the end of the day
- Ease of handling/insertion
- Ease of handling/removal
- Dryness
- Vision upon insertion
- **Vision**
- Vision in low light
- Vision at end of day
- Lens cleanliness upon removal
- Overall impression

A summary of rewetting drop usage by visit and by highest (i.e., most) use over all scheduled follow-up visits will be provided.

### **Symptoms/Complaints**

For each visit, each symptom/complaint will be summarized as follows:

- 1) Categorically by rating (i.e. 0 – None, ..., 4- Severe)
  - a. This summary will include the number and proportion of eyes experiencing any symptoms of problems with the lenses

- 2) Positive reports (i.e. symptoms/complaints reported as > 0 None) by visit for each of test/control by study completion/discontinuation status.
- 3) By favorable / unfavorable, where favorable is defined as a rating < 3 or choosing “No” symptoms or problems with the lenses, and unfavorable is defined as a rating of 3 or 4.

Note this will include the symptoms/complaints for the habitual lenses as collected at the screening visit

### **Slit-Lamp Examination**

Results from the slit-lamp examination will be summarized categorically (typically grade 0 – 4 or absent/present, depending on category) for each slit-lamp examination category at each scheduled visit. Additionally, for each visit, the total findings across categories of each grade (for categories graded 0 – 4) will be summarized categorically. This will be done for each of test/control by study completion/discontinuation status.

### **Corneal Scars**

The number and percentage of eyes with pre-existing corneal scars will be summarized, as well as the number percentage of eyes developing new corneal scars or experienced changes to their pre-existing scars. The locations of the scars will be summarized by visit and overall (categorical) along with the size in millimeters of the largest scar observed at that visit (or overall).

A corresponding listing with details of each pre-existing, new, or changed corneal scar will be produced.

### **Corneal Infiltrates**

Corneal infiltrates will be summarized at each scheduled visit. This summary will include:

- Size of largest infiltrate (mm)
- Depth of deepest infiltrate (as epithelial, anterior stroma, or mid/posterior stromal)
- Infiltrate density (Grade 0 – 4)
- Infiltrate type
- Degree of pain (categorically as 0 – 10)
- Size of any overlying defect (mm)
- Location

### **Pregnancy Status**

A listing of subjects who become pregnant will be provided.

#### **4.9.1. Subgroup analyses**

Several analyses will be repeated for each lens group. The groups are the same as described in Table 3. The analyses which will be repeated as subgroup analyses on these lens groups include:

- All primary analyses
  - Slit-lamp findings > Grade 2 over all follow-up visits
  - Front Surface Deposits with grade of  $\leq 2$  over all follow-up visits

- Overall comfort over all follow-up visits
- Vision over all follow-up visits
- Symptoms/complaints

#### **4.10. Changes to Protocol-Planned Analyses**

Included a tipping point analysis to primary safety endpoint of proportion of eyes with any slit-lamp findings greater than Grade 2 over all follow-up visits. There are no other planned changes to the protocol-planned analyses.

## 5. Supporting Documentation

### 5.1. Appendix 1: Algorithms for Refraction Parameters and LogMAR

#### Refraction Parameters

Results originally given in positive cylinder notation (i.e., with a cylinder value  $> 0$ ) can be converted to minus notation by the following algorithms:

- Sphere = original sphere + original cylinder
- Cylinder =  $-1 \times$  (original cylinder)
- Axis:
  - If original axis is between 1 and 90, inclusive ( $1 \leq \text{original axis} \leq 90$ ), then new axis = original axis + 90
  - If original axis is between 91 and 180 ( $91 \leq \text{original axis} \leq 180$ ), then new axis = original axis - 90

Spherical equivalent is calculated as sphere + 0.5\*cylinder, where cylinder and sphere are in minus notation.

#### Determining LogMAR from the number of letters correct.

- Let X be the number of letters entered on the case report form. Then logMAR is as follows:

If  $X \geq 7$  then  $\text{logMAR} = 0.8 - (0.02 * [X - 7])$ ;

Else if  $X < 3$  then  $\text{logMAR} = 1.0 - 0.0333 * X$ ;

Else if  $3 \leq X < 7$  then  $\text{logMAR} = 0.9 - (0.025 * [X - 3])$ ;

